- Pregnant or nursing women, this is to avoid any potential risks to their health or that of their infants.
- Individuals who were actively taking drugs that could alter pain perception or anxiety levels, such as nonsteroidal anti-inflammatory drugs, opioids, or antidepressants. This was to ensure that the study's findings on pain perception were not influenced by external substances
- Individuals with heavy alcohol consumption. .
- Patients with active pathologies at the injection site, this is to avoid complications and to ensure the accuracy of the study's results.
- Individuals who could not commit to the study's schedule or were unable to give informed consent. This ensured that all participants were fully aware of and agreeable to the study's procedures and requirements.
- Patients who required intravenous sedation for their dental procedures.

Sample Size

The study was designed with a carefully considered sample size to ensure statistical significance and reliability of the results. The sample size for the study was determined utilizing the G-power calculator, resulting in a decision to allocate 40 participants to each of the two groups, with each participant receiving two different injections, thereby evaluating 80 sites in total. This approach allowed for a comprehensive comparison between the two injection types, as each patient served as their control.

Study Design

The study commenced with an initial assessment to determine patient eligibility. Once eligibility was confirmed, the patient was scheduled for their first injection, during which their baseline heart rate was measured before any procedures. Following this, the patient received the first local anaesthesia injection using one of the two methods being compared in the study. After the injection was administered, the patient's heart rate was measured again to record any changes that may have occurred due to the injection then the patient will be asked to evaluate pain intensity with Visual Analogue Scale.

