The patient then returned after one hour, and the patient's heart rate being recorded before the administration of local anaesthesia. For this second injection, the alternative injection method was used on the other side, ensuring that each patient experienced both types of injections. Following the second injection, the patient's heart rate was measured once more to capture the immediate physiological response and the patient will be asked again to evaluate pain intensity with Visual Analogue Scale.

[figure not shown]

Figure 1: Flow chart of the study

This study design is a split mouth clinical trial which allowed for a within-subjects comparison, where each patient's reaction to both injection methods could be directly compared. The heart rate measurements before and after each injection provided objective data on the physiological response to the injections.

Steps of the Experiment

The experimental protocol was meticulously structured to evaluate the efficacy and patient response to two different local anaesthetic delivery systems. The steps were as follows:

Step I: Before administering a local anaesthetic, the patient's heart rate was checked with a pulse oximeter (Beurer Finger Pulse Oximeter). The results were recorded.

Step II: Patients were randomly assigned to get the injection of local anaesthetic at their initial appointment either with the Dentapen system (ramp-up) or with Vibraject. To simplify the protocol, a 27-gauge needle was used for all dental injections with bevel side directly headed to the injected site.

Step III: In the next appointment, after one hour on a digital timer, the other technique was used for the same patients on the other side. Hence, each patient was given local anaesthesia twice, once with the Dentapen system (ramp-up mode) and once with Vibraject.

Step IV: Immediately after each local anaesthesia injection operation, the patient was asked to use the Visual Analogue Scale to score the intensity of reported pain.

Step V: After administering a local anaesthetic, the patient's heart rate was measured with a pulse oximeter (Beurer Finger Pulse Oximeter). The results were recorded.

Step VI: After both injections were administered to each patient, they were asked which injection they would prefer by selecting the injection number (first or second) according to their order for each patient.

Risk of Bias

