Figure 2: Dentapen used in the study.

Injection with Vibraject

After drying the mucosa, a cotton-tipped applicator with a 20% benzocaine gel (Topox; Sultan Healthcare, Inc., York, PA) was placed for 60 seconds using a digital timer. After 60 seconds, the target site was wiped with another 2-inch by 2-inch cotton gauze and injecting 0.5 cartridge (0.9 mL) of 3% mepivacaine hydrochloride with no epinephrine (Henry Schein, Melville, NY) which was stored in room temperature. The needle was advanced into the tissue until it was estimated to be over the root apex while remaining parallel to the tooth's long axis. The Vibraject was activated after aspiration to deposit the solution slowly at approximately 50 seconds (time necessary to infiltrate 0.5 mL of anesthetic with the dentapen system) for both groups. The time factor was therefore limited to prevent a possible confounding effect in the patients' pain perception. Following cartridge deposition, the operator adjusted the participant to an upright

seated position so that he or she could independently record his or her perceived pain on the Visual Analogue Scale. The Vibraject was selected as the vibrator due to its simple design, battery operation, and ability to be easily attached to a syringe with minimal adjustment to conventional injection procedures. Also, compared to other vibration gadgets, it is reasonably affordable.

Figure 3: Vibraject used in the study.

Visual Analogue Scale scale

The Visual Analogue Scale score was stratified into distinct categories: "0" denoted absence of pain, scores ranging from "1-3" indicated mild pain, "4-6" signified moderate pain, "7-9" represented severe pain, and the maximum score of "10" was designated as indicative of the utmost intensity of pain conceivable.

Statistical Analysis

The statistical analysis for this study was conducted using SPSS Version 20 (IBM-SPSS Inc., Chicago, IL), a robust statistical software package that allows for detailed data management and analysis. The primary statistical tests employed were the paired T-test for analysing the heart rate data and the Wilcoxon test for the Visual Analogue Scale pain scores.

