The paired T-test was chosen for the heart rate data as it is designed to compare the means of two related groups, such as the same patients' heart rates before and after each injection. This test is particularly suitable for assessing whether there is a statistically significant change in heart rate following the administration of local anaesthesia.

For the Visual Analogue Scale pain scores, the Wilcoxon test was utilized. This non-parametric test is ideal for data that are not normally distributed and is used for comparing two related samples, matched samples, or repeated measurements on a single sample. In this study, it was employed to evaluate the differences in pain scores between the two different injection techniques on the same patients.

A p-value of 0.05 or less was considered statistically significant. This conventional threshold indicates that there is only a 5% likelihood that the observed differences occurred by chance. Thus, if the p-value is less than or equal to 0.05, the results are deemed statistically significant, suggesting a real difference between the two techniques that is not due to random variation.

RESULTS

Table 1 shows the demographic characteristics of the study population, offering insights into both age and gender distribution. The mean and standard deviation for age provides a central tendency and variability measure, while the gender distribution details the proportion of males and females in the sample. The mean age of the patients was 36.1 (SD 9.33) years, with the majority being males (87.5%).

Table 1: Descriptive statistics of study participants (N=40), highlighting age and gender distribution

Study variables	N (%)
Age in years (mean \pm SD)	36.1 \pm 9.33
Gender	
• Male	35 (87.5%)
• Female	05 (12.5%)

Figure 4 presents the study population's preferred method for injecting anaesthesia. The highest number of the participants showed interest in the Dentapen® method (n = 25, 62.5%) while 15 participants showed inclination towards the Vibraject method (37.5%).

[figure not shown]

Figure 4: Preferred method of injecting local anaesthesia by the study population

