Table 2 demonstrates descriptive statistics related to heart rate measurements, including mean, standard deviation, and standard error of the mean for different conditions. The mean heart rate before treatment is slightly lower for Dentapen® (70.225) compared to Vibraject (70.775). The mean heart rate after treatment is higher for Dentapen® (71.75) compared to Vibraject (71.05). Both Dentapen® and Vibraject showed an increase in mean heart rate after treatment.

Table 2: Heart rate before and after the procedure

		Mean	N	Std. Deviation	Std. Error Mean
Overall	Heart rate before	70.5000	80	10.16572	1.13656
	Heart rate after	71.4000	80	9.59905	1.07321
Dentapen®	Heart rate before	70.2250	40	10.04984	1.58902
	Heart rate after	71.7500	40	9.94794	1.57291
Vibraject	Heart rate before	70.7750	40	10.40091	1.64453
	Heart rate after	71.0500	40	9.35058	1.47846

Table 3 indicates a statistically significant increase in mean heart rate measurements following Dentapen® injection ($p=0.010$). However, no significant differences were observed in the mean heart rate measurements between the overall and Vibraject before and after injection ($p>0.05$).

Table 3: Comparison of mean heart rate measurements before and after injections with Dentapen® and Vibraject

	Paired Differences					t	P-value §
	Mean	Std. Deviation	Std. Error	95% Confidence Interval of the Difference			

						Lower	Upper		
Overall	Heart rate before - Heart rate after	- .90000	4.18133	.46749	-1.83051	.03051	- 1.925	0.058	
Dentapen®	Heart rate before - Heart rate after	- 1.5250	3.56613	.56386	-2.66550	-.38450	- 2.705	0.010 **	
Vibraject	Heart rate before - Heart rate after	- .27500	4.67940	.73988	-1.77155	1.22155	-.372	0.712	

§ P-value has been calculated using paired sample t-test.

** Significant at p<0.05 level.

Table 4 depicts the mean Visual Analogue Scale score. The mean score of Vibraject (2.175) was observed higher than that of Dentapen (1.550). However, the results yielded an insignificant difference (p=0.105). The overall mean Visual Analogue Scale score was 1.863.

Table 4: Comparison of Visual Analogue Scale between Dentapen® and Vibraject

	Mean	N	Std. Deviation	Std. Error Mean	P-value §
Overall	1.863	80	1.605	0.179	
Dentapen®	1.550	40	1.467	0.232	0.105
Vibraject	2.175	40	1.693	0.268	

§ P-value has been calculated using Mann Whitney Z-test.

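### Table 4 credits the pain-score p-value of 0.105 to a Mann-Whitney test, although the analysis section specifies a related-samples Wilcoxon test on the same 40 patients

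*Combined protocol and SAP*

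**What the plan says.** The Statistical Analysis section names "the Wilcoxon test for the Visual Analogue Scale pain scores". Taken alone, Wilcoxon could mean the rank-sum test, which is equivalent to Mann-Whitney. The same section rules that reading out: it says that the test "is used for comparing two related samples, matched samples, or repeated measurements on a single sample" and that "it was employed to evaluate the differences in pain scores between the two different injection techniques on the same patients". Only the signed-rank test fits that description.

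The design agrees. Study Design states: "This study design is a split mouth clinical trial which allowed for a within-subjects comparison". Sample Size gives the reason for the comparison, "as each patient served as their control", and describes the data as 40 participants, "with each participant receiving two different injections, thereby evaluating 80 sites in total".

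In the Results, Table 4 lists 40 scores for Dentapen (mean 1.550, SD 1.467), 40 for Vibraject (mean 2.175, SD 1.693) and 80 overall, with p = 0.105. The footnote reads "P-value has been calculated using Mann Whitney Z-test". The sentence above the table draws the conclusion from that p-value: "the results yielded an insignificant difference (p=0.105").

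**The concern.** Mann-Whitney compares two independent groups. The two rows of Table 4 are the same 40 patients measured twice, so the footnoted test ignores the pairing on which the split-mouth design rests. No paired VAS difference, signed-rank statistic or reason for a change of test appears anywhere.

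This is the only formal comparison between the devices. Table 3 tests heart rate before against after within each device, and preference (25 against 15) is given as counts without a test. If Mann-Whitney was run, the specified test could give a smaller or a larger p-value. Positive within-patient correlation would tend to lower it, and negative correlation would tend to raise it. With positive correlation, the unpaired test can miss a difference that the paired test would detect.

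**Working it through.** **1. Check of Table 4.** With SE = SD/√n:
- 1.467/√40 = 0.232, 1.693/√40 = 0.268 and 1.605/√80 = 0.179, all as printed.
- Overall mean = (1.550 + 2.175)/2 = 1.8625.
- Overall SD = √{[39(1.467²) + 39(1.693²) + 80(0.3125²)]/79} = 1.605.

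The summaries are consistent. The p-value of 0.105 cannot be recomputed, because a rank test needs the patient-level scores.

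**2. Unpaired analogue.** t = 0.625/√(1.467²/40 + 1.693²/40) = 0.625/0.354 = 1.76, two-sided p = 0.082. (The document does not state sidedness; two-sided is assumed throughout.)

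**3. Paired analogue.** SD of the differences = √(1.467² + 1.693² − 2r × 1.467 × 1.693), and t = 0.625/(SD/√40) on 39 df. The value of r is assumed.

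| r | SD of differences | t | p |
|---|---|---|---|
| −0.3 | 2.551 | 1.549 | 0.129 |
| 0 | 2.240 | 1.765 | 0.0855 |
| 0.2 | 2.006 | 1.970 | 0.056 |
| 0.3 | 1.878 | 2.104 | 0.042 |
| 0.4 | 1.741 | 2.270 | 0.029 |
| 0.5 | 1.592 | 2.483 | 0.017 |

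The p-value crosses 0.05 at r of about 0.24 and equals 0.105 at r of about −0.13. This is background only, since the specified test is a rank test.

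**4. Rank tests in simulated trials.** Scores from 0 to 10 were drawn from beta-binomial distributions matched to the Table 4 means and SDs and linked by a Gaussian copula. There were 40,000 trials of 40 patients per correlation. P-values were asymptotic and tie-corrected, and zero differences were dropped. Trials with a Mann-Whitney p of 0.095 to 0.115 were kept (1,365 to 2,238 per setting). Here r describes the simulated population, not the single sample.

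| r | median signed-rank p | share at or below 0.05 |
|---|---|---|
| −0.18 | 0.135 | 2% |
| 0 | 0.105 | 10% |
| 0.18 | 0.076 | 28% |
| 0.27 | 0.060 | 41% |
| 0.37 | 0.046 | 54% |
| 0.47 | 0.030 | 73% |

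**5. Data sets that reproduce Table 4.** If scores are whole numbers, as the VAS categories suggest, Table 4 fixes the totals:
- Dentapen: sum 40 × 1.550 = 62; sum of squares 39(1.467²) + 62²/40 = 180.
- Vibraject: sum 40 × 2.175 = 87; sum of squares 39(1.693²) + 87²/40 = 301.

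Enumeration gives 545 and 3,726 possible score distributions. Drawing pairs of them with beta-binomial weights gives a Mann-Whitney p with median 0.086 and central 95% range 0.057 to 0.106. So 0.105 is possible, but near the upper edge. Pairs with a Mann-Whitney p of 0.1045 to 0.1055 were then matched patient to patient at random. Here r is the correlation observed in the 40 pairs.

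| observed r | median signed-rank p | share at or below 0.05 |
|---|---|---|
| −0.2 | 0.128 | 0% |
| 0 | 0.097 | 1% |
| 0.2 | 0.063 | 21% |
| 0.3 | 0.048 | 56% |
| 0.4 | 0.033 | 95% |
| 0.5 | 0.020 | 100% |

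Repeat runs agree to within sampling error.

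**6. Could 0.105 already be the signed-rank result?** The same enumeration was used without conditioning on Mann-Whitney. A signed-rank p of 0.1045 to 0.1055 occurred in about 0.9% to 1.3% of pairings at observed r = 0, about 0.6% to 1.1% at 0.1, and 0% to 0.15% at 0.2, across separate runs. A Mann-Whitney p in that window occurred in about 0.7% of matched pairs. At r of about 0.1 or less, the summaries therefore do not favour either test. At r of 0.2 or more, they count against a mere mislabel.

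**The case against.** The strongest reply is that the footnote is a slip. The Statistical Analysis section is written in the past tense and says that the Wilcoxon test was used, so the document makes two statements about what was done, and the fuller one is the correct one. Step 6 shows that Table 4 cannot exclude this at low or negative r. If so, the p-value and conclusion stand and only a label changes. This possibility remains open, but the reader cannot confirm it. The Table 3 footnote names the paired t-test as specified, so footnotes in this document do identify tests.

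A second reply is that the reversal is hypothetical. No within-patient VAS correlation or proxy is given, and at r of 0 or below the conclusion changes in at most 10% of cases. That is correct, and no claim is made here that the planned test would be significant.

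A third is that ignoring positive correlation generally makes the test conservative, and no superiority on pain is claimed. This gives limited comfort when the reported finding is the absence of a significant difference, because a conservative test can hide one.

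Finally, reversal at r of 0.4 is near certain only in step 5. Step 4 gives 54% at 0.37 and 73% at 0.47. The two differ because step 5 uses observed r and conditions more tightly on Table 4. The step 5 figures should be read against the correlation in the actual 40 pairs.

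**Conclusion.** The concern holds. The test named under Table 4 contradicts both the specified analysis and the paired design, and nothing in the document reconciles them. The non-significant pain comparison is therefore not shown to be the planned result.

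If Mann-Whitney was run, the conclusion would most likely stand at zero or negative r and is uncertain at r of about 0.2 to 0.35. It would very likely reverse at an observed r of about 0.4 or more. These figures assume two-sided asymptotic tests with zero differences dropped, beta-binomial score shapes and, in step 5, whole-number scores. If the footnote is mislabelled, 0.105 stands and only the label is wrong. Because the only between-device test is affected, this must be settled before the result is relied on.

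**What to change.** Run, or confirm, the Wilcoxon signed-rank test on the 40 within-patient differences (Dentapen minus Vibraject), and state how zero differences are handled. If the result differs from 0.105, correct the p-value, the footnote and the sentence above Table 4. If 0.105 proves to be the signed-rank result, correct only the footnote. Reporting the Hodges-Lehmann median difference with a 95% confidence interval would also show the size of the effect. This is good practice, but the contradiction can be resolved without it.

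The cost is one analysis on data already collected, plus a corrected table, footnote and sentence. No new patients are needed.
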